14. APPENDICES

Appendix 1 Validated Investigator 4-point Photographic Scale of Lateral Canthal Line Severity (LCL-ILA)

Doc id

Print date:

MA-40370

2020-06-11 13:03

Lateral Canthal Line Investigator Live Assessment (LCL-ILA) **Dynamic**

O None

Smooth skin, no lines that are immediately noticeable.

1 Mild

Lines that are noticeable but not pronounced.

2 Moderate

Lines that are immediately noticeable and pronounced. 3 Severe

Lines that are immediately noticeable and extremely

Effective date: 2020-06-10 11:38

Effective date: 2020-06-10 11:38

43QM1901 Clinical Study Protocol - QM1114 - LCL

[figure not shown]
Doc id

Print date:

MA-40370

2020-06-11 13:03

Appendix 2 Validated Subject 4-point Photographic Scale of Lateral Canthal Line Severity (LCL-SLA)

[figure not shown]

Effective

2020-06-11 13:03

Doc id 43QM1901 Clinical Study Protocol - QM1114 - LCL ♣ GALDERMA MA-40370

Lateral Canthal Line (Crow's Feet) Subject Live Assessment (LCL-SLA) **Dynamic**

Level 0

Smooth skin, no lines that are immediately noticeable.

Level 1

[figure not shown]
Lines that are noticeable but not pronounced.

Level 2

Lines that are immediately noticeable and pronounced.

Level 3

Lines that are immediately noticeable and extremely pronounced.

Effective date: 2020-06-10 11:38

Trile 43QM1901 Clinical Study Protocol - QM1114 - LCL

MA-40370

[figure not shown]
Doc id

Effective

GALDERMA

Title
43QM1901 Clinical Study Protocol - QM1114 - LCL

MA-40370

Effective date: 2020-06-10 11:38

Trile 43QM1901 Clinical Study Protocol - QM1114 - LCL

MA-40370

[figure not shown]
Doc id

Effective

Trile 43QM1901 Clinical Study Protocol - QM1114 - LCL

MA-40370

Doc id

Trile 43QM1901 Clinical Study Protocol - QM1114 - LCL Doc id

Print date:

MA-40370

2020-06-11 13:03

Effective

Effective date: 2020-06-10 11:38

Version: 4.0

Investigator Signature

	43QM1901 Clinical Study Protocol - QM1114 - LCL	Doc id
♣ GALDERMA	Togramor Charles Study Frontier Quarter Deb	MA-40370

Print date:

2020-06-11 13:03

Appendix 6 Focused Physical Examination Form Example		
Not done Provide detail	s:	
General Health Assessment: Complete at Screening, Baseline (prior to treatment), Day 7, Day 14, Months 1, and 6/ET Question the subject about their general health (general wellbeing/ bodily functions, e.g., arms, legs, stomach/ bladder, bowel, also refer to the list of Adverse Events Potentially Suggestive of Distant Spread of Toxin (Appendix 7). Abnormalities noted pre-injection should be recorded as medical history and Investigator should confirm if any abnormalities affect subject eligibility. Abnormalities noted post-injection should be documented as AEs. Next, proceed to the Focused Physical Examination (Part 1 and 2) as indicated below. Part 1: Complete at Screening, Baseline (prior to treatment), Day 7, Day 14, Months 1, and 6/ET		
Please perform a targeted examinat	ion of the fac	ee, head, and neck recording abnormalities.
Part 1 Examination	Normal	Abnormal* (provide details)
Eyelid position		
Eyebrow position		
Vision abnormalities (not refractive errors)		
Throat function (e.g., swallowing/drink water)		
Ability to talk and chew		
Ability to stick out and move tongue		
Ability to lift shoulders		
	ld confirm	paseline visit, noted pre-injection, should be recorded as medical if any abnormalities affect subject eligibility. Abnormalities noted as AE.

Date

•	43QM1901 Clinical Study Protocol - QM1114 - LCL	Doc id
GALDERMA		MA-40370

Print date:

2020-06-11 13:03

PART 2: Complete at Day 7, Day 14, Months 1, and 6/ET		
Not done Provide details:		
After questioning the subject about their general health and performing Part 1, determine if there are any clinically significant abnormalities that may suggest local or remote spread of toxin effect. - Local Spread of Toxin Effect refers to effects in areas adjacent to the treatment area (e.g., lower frontalis, glabellar area, medial part of temporalis). - Remote Spread of Toxin Effect refers to effects in other body parts, not adjacent to the treatment area, when effect can only be attributed to the toxin and there is no other medically sound cause. - Determine if the event is clinically significant (i.e., would affect subject safety, confound the study data, or requires medical treatment) and document on the source document. Please refer to the list of remote spread of toxin events (Appendix 7) while doing clinical evaluations based on subject's symptoms and signs. Directed questioning and examination will then be performed as appropriate. If yes, please describe.		
Part 2 Examination	No	Yes* (provide details)
Targeted Physical Examination of Face and Neck to Evaluate Local Spread of Toxin Effect Local spread of toxin effect event(s) observed? General Physical Examination to Evaluate		
 Remote Spread of Toxin Effect Remote spread of toxin effect event(s) observed? 		
* Abnormalities should be documented as Al Additional comments for Focused Physical E		
Investigator Signature		Date

GALDERMA
Title
43QM1901 Clinical Study Protocol - QM1114 - LCL
MA-40370

Print date:

2020-06-11 13:03

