5. SELECTION AND DISPOSITION OF CLINICAL STUDY POPULATION

5.1 Number of Subjects

As a screen failure rate of approximately 10 percent is anticipated, approximately 330 subjects will be screened in order to get 300 subjects enrolled in a 3:1 ratio to QM1114-DP 60 U (N=225) or placebo (N=75). It is expected that each center will recruit a similar number of subjects.

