6.4 Blinding

This is a double-blind study in which neither the Investigator, sub-Investigator, study staff, nor the subject will know the subject's study product assignment (i.e., QM1114-DP or placebo). Placebo is identical in appearance to QM1114-DP but contains no active drug substance.

Subjects will be randomized at baseline to either treatment with QM1114-DP or placebo. In order to maintain the blind, the study products, QM1114-DP and placebo, will be supplied in identical vials, each with a unique number on the vial label. Both QM1114-DP and placebo will be administered in exactly the same way.

An un-blinded statistician will generate the randomization schedule; however, he/she will not be involved in any other aspect of the study prior to database lock.

sion: 4.0

Print date:

2020-06-11 13:03

The Sponsor's staff or designees directly involved in clinical operations management, data management, and statistical evaluation of the study will remain blinded until the database is locked, unless emergency unblinding is required.

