7.2.6.1 Definitions

7.2.6.1.1 Adverse Events (AE)

According to ICH E2A, ¹⁵ an AE is any untoward medical occurrence in a patient or a clinical investigation subject administered a pharmaceutical product and which does not necessarily have a causal relationship with this treatment. An AE can therefore be any unfavorable and unintended sign (including an abnormal laboratory finding), symptom, or disease temporally associated with the use of a medicinal (investigational) product, whether or not related to the medicinal (investigational) product.

Thus, any new sign, symptom or disease, or any clinically significant worsening of an existing sign, symptom or disease (including new episodes of a chronic disease [e.g., hay fever, allergy]) compared to the condition at the first visit, should be considered as an AE. Lack of efficacy is not considered as an AE.

	43QM1901 Clinical Study Protocol - QM1114 - LCL	Doc id
- GALDERMA	45QMI761 CHIRCH Study 1100Col - QMI114 - LCL	MA-40370

2020-06-11 13:03

Notes:

- There should be an attempt to report a diagnosis rather than the signs, symptoms or abnormal laboratory values associated with the report of an AE. However, a diagnosis should be reported only if, in the Investigator's judgment, it is relatively certain. Otherwise, symptoms, signs, or laboratory values should be used to describe the AE.
- Pregnancy is not to be considered as an AE; however, is an important medical event that must be monitored as described in Section 7.2.6.2.3.
- The effects of all BoNT products may spread from the area of injection to produce symptoms consistent with BoNT effects. These symptoms have been reported hours to weeks after injection. Remote spread of toxin that affects swallowing and breathing can be life threatening, and there have been reports of death. The risk of symptoms is increased in subjects who have underlying conditions (e.g. disorders of the neuromuscular junction) that would predispose them to these symptoms. BoNT is contraindicated in individuals with known hypersensitivity to any BoNT preparation or to any of the components in the formulation.

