7.2.6.1.7 Relationship to the Study Product and/or Clinical Study Procedure

The Investigator is to determine whether there is a reasonable causal relationship between the occurrence of the AE and exposure to the study product and/or clinical study procedure.

Medical judgment should be used to determine the relationship, considering all relevant factors including the pattern of reaction, temporal relationships, relevant medical history, and confounding factors such as co-medication or concurrent diseases.

The expression "reasonable causal relationship" is meant to convey in general that there are facts or arguments to suggest a causal relationship (ICH E2A, Section IIIA 1).

The relationship assessment for an AE is to be completed using the following definitions as a guideline:

Reasonable Possibility: According to the reporting Investigator, there is a reasonable possibility (i.e., suggestive evidence or arguments) that there is a causal relationship irrespective of the dose administered between:

- The study product (active or placebo) and the AE.
- The clinical study protocol procedure (e.g., bruising or marks from blood draws, injection related trauma, etc.) and the AE.

A two-point scale (Yes or No response) shall be used for the causality assessment. The Investigator shall be asked to indicate a response to each of the following questions in the eCRF:

- "Do you consider that there is a reasonable possibility that the event may have been caused by the study product?", and
- "Do you consider that there is a reasonable possibility that the event may have been caused by the study product injection procedure?"

If any of these questions is answered Yes, the AE is considered related.

No Reasonable Possibility: No suggestive evidence or arguments can be identified regarding a causal relationship between the study product or the clinical study protocol procedure and the AE.

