2.5.2.2 Assessment of local/remote toxin spread and hypersensitivity

Any potential or suspected toxin spread or toxin hypersensitivity events will be evaluated separately. The same methods specified in Section 2.5.2 will be followed. Suspected toxin spread events and suspected hypersensitivity events will be summarized in separate tables. The investigator will conduct the investigation and evaluate if an AE is also a suspected toxin spread or hypersensitivity event; however, Appendix 7 in the CSP lists AEs potentially suggestive of spread of toxin.

Print date:

2021-04-15 15:20

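### The site form's sole-attribution definition of remote toxin spread conflicts with the form's own instruction and with the SAP, so remote spread may be under-labelled; the SAP should add a by-arm summary of Appendix 7 terms

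*Protocol*

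**What the plan says.** **The form (Protocol Appendix 6, Part 2).** The examiner is first told to "determine if there are any clinically significant abnormalities that may suggest local or remote spread of toxin effect". The form then defines the two kinds of spread. Local spread is defined by place alone: "Local Spread of Toxin Effect refers to effects in areas adjacent to the treatment area". Remote spread means effects elsewhere in the body, but only "when effect can only be attributed to the toxin and there is no other medically sound cause". The site then answers yes or no to whether remote spread was observed.

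**The SAP (2.5.2.2).** Potential or suspected toxin-spread events are evaluated separately, and suspected spread events get their own table. On who decides, it says: "The investigator will conduct the investigation and evaluate if an AE is also a suspected toxin spread or hypersensitivity event". It notes that protocol Appendix 7 lists suggestive events, but it does not use that list to select events for the table.

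**The setting.** Under Protocol 6.4, "neither the Investigator, sub-Investigator, study staff, nor the subject will know the subject's study product assignment". Protocol 5.1 plans 225 subjects on QM1114-DP and 75 on placebo.

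**The risk.** Protocol 7.2.6.1.1 states: "Remote spread of toxin that affects swallowing and breathing can be life threatening, and there have been reports of death".

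**The concern.** The form holds two standards in one paragraph. The instruction is broad, while the definition of remote spread asks the investigator to exclude every other explanation. A blinded investigator knows that one subject in four had no toxin, so it is hard to say that an effect can have no cause but toxin. Part 1 of the form checks vision, swallowing, talking and chewing, and mild changes there often have another plausible explanation. A site that follows the definition to the letter may answer no to an event that the SAP would want to see as suspected.

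The SAP names no other way into the table: no search by preferred term and no independent review. If the investigator carries the form's definition over into the SAP classification, a table with few or no remote-spread events could partly reflect the wording of the form. That matters because spread is a risk of the whole product class and the protocol itself describes it as potentially fatal.

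**Working it through.** The plan states no figure on this point, so there is nothing to reproduce. The check is a comparison of the texts, followed by an illustration.

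**Comparison of the standards**

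| Place | What it governs | Standard |
|---|---|---|
| Appendix 6 Part 2, instruction | What the examiner looks for | Abnormality that may point to spread |
| Appendix 6 Part 2, local spread | Label | Location only |
| Appendix 6 Part 2, remote spread | Label | Sole attribution to toxin, other causes excluded |
| SAP 2.5.2.2 | Entry into the spread table | Potential or suspected, judged by the investigator |
| Protocol 7.2.6.1.7 | Causality of any AE | Reasonable possibility |

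The first four rows concern spread, and the third does not fit the first or the fourth. The fifth asks a different question and is not a definition of spread.

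**What is recorded regardless of the label.** Protocol 7.2.1 and Appendix 6 require post-injection abnormalities to be recorded as AEs. SAP 2.5.2 tabulates all TEAEs by SOC and PT for each treatment group. The events are therefore present, term by term, in both arms. No table pools the Appendix 7 terms, so a few events spread over several terms would give no class-level comparison.

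**Illustration of sensitivity to labelling.** Inputs from the documents: n = 225 on active and 75 on placebo (75/300 = 25%). Assumed, because the documents give neither: the fraction s of true remote-spread events that gets labelled (100% to 10%) and the true rate r (1% shown).

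- Upper one-sided 95% limit for the labelled rate with 0/225: 1 − 0.05^(1/225) = 0.0132, or 1.3%.
- The labelled rate is r × s, so the limit for the true rate is 0.0132/s.
- Chance of at least one labelled event: 1 − (1 − r × s)^225.

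| s (assumed) | Limit for true rate given 0/225 | Expected labelled events at r = 1% | Chance of at least one at r = 1% |
|---|---|---|---|
| 100% | 1.3% | 2.25 | 90% |
| 50% | 2.6% | 1.13 | 68% |
| 25% | 5.3% | 0.56 | 43% |
| 10% | 13% | 0.23 | 20% |

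With s = 50%, the chance of at least one labelled event is 43% at a true rate of 0.5% and 90% at 2%. The last row is an extreme: 13% of 225 is about 30 subjects, whose events would also be visible in the ordinary TEAE tables. The figures describe what the labelled table alone could show. They do not measure what the trial could miss.

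**The case against.** The strongest reply is that the SAP does not adopt the form's wording. SAP 2.5.2.2 does not cite Appendix 6 or its yes/no box. Its own scope is wide, and the only protocol item it cites is Appendix 7. Nothing says that a no on the form keeps an event out of the table. This stands. A reader might infer that the table rests solely on the form's test; the documents do not support that. They support an unreconciled conflict, with the form's definition the only written definition of remote spread in the sections cited here.

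A reader might also count Protocol 7.2.6.1.7 as a third threshold for the same event, since it asks whether "there is a reasonable possibility (i.e., suggestive evidence or arguments) that there is a causal relationship". That section sets the causality question for every AE and does not define spread. It also treats injection-procedure causation as related, so copying it unchanged into a definition of toxin spread would blur that definition.

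Three further points stand. Local spread carries no sole-attribution test. The form is headed as an example and directs the examiner to Appendix 7. The underlying events are compared by arm in the TEAE tables, without reference to the spread label.

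What the reply does not remove is the mismatch between the form's definition and both its own instruction and the SAP's scope, or the absence of any rule-based route into the spread table.

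**Conclusion.** The concern holds in limited form. A site that applies the form's definition literally, under the blind, may under-label remote spread, and the remote-spread entries in the SAP's table may then be incomplete. How investigators would read the form is an inference. The content of Appendix 7 was not available for this point, so whether it carries a labelling instruction is open.

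A reader might go further and conclude that investigators can hardly ever meet the test, or that the class risk will be under-counted. The documents do not support either. They give no labelling fraction and no true rate, the SAP asks for suspected events, and the events remain in the by-arm TEAE tables. The 1.3% and 2.6% limits are illustrations, and the second assumes that half of true events are labelled.

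The change is worth making because the risk is serious and the cost is small. No efficacy result is affected.

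**What to change.** 1. In SAP 2.5.2.2, pre-specify before unblinding a by-arm summary of every TEAE whose preferred term matches the protocol Appendix 7 list, whatever the investigator's label. Show the investigator-flagged events alongside. This gives a comparison by randomised arm that does not depend on a blinded judgement of attribution.
2. In Appendix 6 Part 2, reconcile the definition of remote spread with the form's own instruction and with the scope of SAP 2.5.2.2, so that one labelling standard applies. This concerns the labelling of events only and leaves treatment and clinical management untouched. If the form can no longer be changed, the first item still works alone.

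The cost is one table from AE data that are already coded, the mapping of Appendix 7 terms to preferred terms, and a wording change on the form. The downside is that some non-specific events with other causes will appear in both arms. The placebo arm helps to read them, but imprecisely: with 75 subjects, even 0/75 has a one-sided 95% upper limit of 1 − 0.05^(1/75) = 3.9%.

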| 2.8 Changes in Analysis Planned in the Protocol | 26 |
| Reference List | 27 |
| Appendix A LCL-ILA Scales | 28 |
| Appendix B LCL-SLA Scales | 30 |
| | |
| | |
| | |
| | |
| Appendix F Schedule of Assessments | 36 |

Print date:

2021-04-15 15:20

1 Study Information

This statistical analysis plan (SAP) describes the efficacy and safety summaries and analyses that will be performed for Clinical Trial Number (CTN) 43QM1901, A Multicenter, Randomized, Double-Blind, Placebo-Controlled Study to Evaluate the Efficacy and Safety of QM1114-DP for the Treatment of Moderate to Severe Lateral Canthal Lines (READY - 2) and is based on the study protocol Version 4 dated 10JUN2020.

1.1 Background

1.1.1 Study design

This is a phase 3, multi-center, randomized, double blind, placebo-controlled study to evaluate the efficacy and safety of 60 units of QM1114-DP for the treatment of moderate to severe lateral canthal lines (LCL).

Each subject will receive a single treatment of QM1114-DP 60 units or placebo divided equally among 6 injection points (0.1 mL per injection point) in the LCL region. Following treatment at baseline, subjects will be monitored for safety and efficacy for 6 months.

1.1.2 Number of subjects and randomization

The study will screen approximately 330 male and female adults, 18 years of age and older, with moderate to severe bilaterally symmetrical LCL at maximum smile in up to 15 study sites in the US and Canada. Following the screening process, eligible subjects will be randomized at the baseline visit (Day 0) in a 3:1 ratio to QM1114-DP or placebo, stratified by site.

1.2 Study Objectives

The objective of the study is to evaluate the efficacy and safety of a single dose of 60 units of QM1114-DP compared to placebo for the treatment of moderate to severe LCL.

1.2.1 Primary efficacy objective

The primary efficacy objective of the study as assessed using the endpoints outlined in Section 1.4.1 is to evaluate a single dose of 60 units of QM1114-DP compared to placebo for the treatment of moderate to severe LCL using the Investigator 4-point Photographic Scale of Lateral Canthal Line Severity (LCL-ILA) (described in Section 1.3.1) and Subject 4-point Photographic Scale of Lateral Canthal Line Severity (LCL-SLA) (described in Section 1.3.2) at maximum smile.

1.2.2 Secondary efficacy objectives

The secondary efficacy objective of the study as assessed using the endpoints outlined in Section 1.4.2 is to evaluate the efficacy of a single dose of 60 units of QM1114-DP compared to placebo for the treatment of moderate to severe LCL using the LCL-ILA.

Print date:

2021-04-15 15:20

| CCI | | |
|-----|--|--|
| | | |
| | | |
| | | |
| | | |
| | | |
| | | |

1.2.4 Safety objective

The safety objective of the study is to evaluate the safety of a single dose of 60 units of QM1114-DP compared to placebo for the treatment of moderate to severe LCL.

1.3 Efficacy assessment

For all assessments, baseline will be defined as the observation that is closest to but prior to study injection on Day 0. Likewise, in general, change from baseline (Δ) will be calculated as the value at a given time point, X, minus the baseline value:

$$\Delta = X Value - Baseline (Day 0) Value$$

1.3.1 Investigator 4-point Photographic Scale of Lateral Canthal Line Severity: Investigator Live Assessment (LCL-ILA)

The LCL-ILA is a 4-point validated scale for assessment of lateral canthal lines (Appendix A). The validated LCL-ILA, developed by Galderma, includes two grading systems: one for Investigator live assessments at maximum smile, CCI

The scale represents LCL severities from none (grade 0), mild (grade 1), moderate (grade 2), to severe (grade 3). Each grade is also depicted by an individual photograph and descriptive text.

The Investigators will use the LCL-ILA for direct, live comparison with the subject's face at at maximum smile. Left and right LCL should be assessed separately at maximum smile. The Investigator will perform the LCL-ILA at:

- Screening/Baseline (prior to treatment) visit(s)
- all post-treatment visits.

Multiple responder indicators will need to be created as follows:

- Primary endpoint LCL-ILA indicator: subjects that achieved a score of 0 or 1 in LCL severity, and had at least 2 grade improvement from baseline at maximum smile at Month 1, for both left and right LCL, will have the value '1'. This indicator will be used in combination with the primary endpoint LCL-SLA indicator to define the primary endpoint composite responder.
- Subjects who achieve a score of 0 or 1 in the LCL-ILA at maximum smile, for both left and right LCL, at each respective post-baseline visit will be considered an LCL-ILA at maximum smile responder for that visit

| | 1 |
|-----|---|
| CCI | |
| CCI | |
| | |
| | |
| | |
| | |
| | |
| | |
| | |

Print date:

2021-04-15 15:20

1.3.2 Subject 4-point Photographic Scale of Lateral Canthal Line Severity: Subject Live Assessment (LCL-SLA)

Similar to the LCL-ILA, subjects will also assess their LCL severity using the LCL-SLA (Appendix B). The validated LCL-SLA, developed by Galderma, includes two grading systems: one for the subject's live assessments at maximum smile, CCI.

The scale represents LCL severities from Level 0, Level 1, Level 2, to Level 3. Each grade is also depicted by an individual photograph and descriptive text.

This subject assessment will be done independently of the Investigator's assessment. Subjects will be asked to evaluate their LCL at maximum smile CCI (left and right side separately) at:

- Screening/Baseline (prior to treatment) visit(s)
- all post-treatment visits

Multiple responder indicators will need to be created as follows:

- Primary endpoint LCL-SLA indicator: subjects that achieved a score of 0 or 1 in LCL severity, and had at least 2 grade improvement from baseline at maximum smile at Month 1, for both left and right LCL, will have the value '1'. This indicator will be used in combination with the primary endpoint LCL-ILA indicator to define the primary endpoint composite responder.
- Subjects who achieve a score of 0 or 1 in the LCL-SLA at maximum smile, for both left and right LCL, at each respective post-baseline visit will be considered an LCL-SLA at maximum smile responder for that visit

2021-04-15 15:20

👶 GALDERMA

Effective date: 2021-02-05 13:17

Effective

Version: 1.0

Title 43QM1901 Statistical Analysis Plan US - QM1114-DP - LCL Doc id MA-43263

Effective date: 2021-02-05 13:17

Effective

GALDERMA

Title
43QM1901 Statistical Analysis Plan US - QM1114-DP - LCL

MA-43263

| CCI | |
|-----|--|
| | |
| | |
| | |
| | |
| | |
| | |
| | |
| | |
| | |
| | |
| | |
| | |
| | |
| | |
| | |
| | |
| | |
| | |
| | |
| | |
| | |
| | |
| | |
| | |
| | |
| | |
| | |
| | |
| | |
| | |
| | |
| | |
| | |
| | |
| | |
| | |
| | |
| | |
| | |
| | |
| | |
| | |
| | |
| | |
| | |
| | |
| | |
| | |
| | |
| | |
| | |
| | |
| | |
| | |
| | |
| | |

Print date:

2021-04-15 15:20

